A proposed randomized clinical trial of the effectiveness of a new breastfeeding- supportive texting program designed specifically for African-American/Black expectant women, as compared to a national maternal health texting program, on rates of exclusive breastfeeding at 2months; Short title: TOPS – Texting to Promote Breastfeeding).

XXXXXXXXXXXXXX

NCT06375655

01/19/2024

Objectives

Specific Aims

- 1. Demonstrate the feasibility and acceptability of a scaled-up program to deliver Team2BF text messages to AA/B expectant women considering breastfeeding.
- 2. Compare breastfeeding outcomes in the group receiving Team2BF with rates among those receiving Bright By Text.
- 3. Compare breastfeeding related knowledge and self-efficacy and social support as moderators of the relationship between the texting intervention and breastfeeding outcomes. (Exploratory aim)
- 4. Compare other key health outcomes (appointment attendance and vaccine receipt and book reading to infant) between the groups to verify that a focus on breastfeeding enhances rather than detracts from general maternal-infant health outcomes. (Exploratory aim)

Study Hypotheses

- Participants will find the Team2BF intervention acceptable as measured by >90%
 continuation, by >75% top score helpfulness of messages for breastfeeding and >75%
 endorsement of friend and family referral.
- 2. Participants receiving Team2BF will have significantly higher exclusive breastfeeding rates at 2 months as compared to participants receiving Bright By Text.
- 3. Breastfeeding knowledge, perceived social support for exclusive breastfeeding and self-efficacy will positively moderate the relationship between texting and breastfeeding outcomes, with those in the Team2BF group demonstrating a significantly greater increase in these domains with time as compared to the Bright By Text group.
- 4. Participants in both groups will have >75% rates of attendance among mothers at the (2-6 weeks) postpartum obstetrical visit and >75% rates of attendance and vaccine receipt for infants at the 2 month (6-12 weeks) well care visit.

Background

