In this research, we follow up on prior work that assessed the feasibility and acceptability and content of a culturally-tuned Breastfeeding-supportive Text Messaging Library intended for AA/B women. That work (TEAM2BF, STUDY20221270) demonstrated that expectant and delivered AA/B women found the text messaging process and content acceptable and helpful. None stopped any or all of the messaging, and approximately 6 messages were revised as recommended by participants. In this current study we aim to obtain preliminary efficacy data by comparing this texting library aimed at promoting breastfeeding to a professionally endorsed national maternal child health texting program, Bright By Text, whose focus is not breastfeeding. By comparing the TEAM2BF texting program to Bright By Text, we can compare whether message content impacts breastfeeding initiation and exclusivity at 2 months. The study design is equitable for participants in that both programs use a similar approach (texting), both are designed to be accessible to minoritized women of low socioeconomic status, and the comparator (Bright By Text) has demonstrated benefits.[16] This study aims to address identified gaps in breastfeeding support for AA/B women that we hope can ultimately reduce racial inequities in breastfeeding rates.

Inclusion and Exclusion Criteria

| | | Inclusion Criteria - mothers |
|--|--|---|
| 1. Expectant women initiating obstetrical care <34 weeks or at any | | Expectant women initiating obstetrical care <34 weeks or at any prenatal visit up |
| | | to 34 weeks gestation |

| 2. | Daily access to a mobile phone with text message capabilities, |
|----|--|
| 3. | 18 years or older (i.e., adult), |
| 4. | Self-identify as African-American/Black, |
| 5. | English speaking, and |
| 6. | Infant feeding plan of "might or will breastfeed". |
| 7. | Receive care at Ahuja Midtown or MAC1200 |

| | Exclusion Criteria |
|--|--------------------------------------|
| 1. | Minors |
| 2. Committed to feeding formula only to their infant | |
| 3. | No mobile phone with text capability |

| | Inclusion Criteria - infants |
|----|--------------------------------|
| 1. | Infant of maternal participant |

| | Exclusion Criteria -infants | |
|----|---------------------------------------|--|
| 1. | 1. Not infant of maternal participant | |

Number of Research Participants

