We will enroll up to 80 participants. Infants are a secondary population and we will enroll up to 85 infants (85 not 80 to allow for inclusion of multiples if this occurs).

Recruitment Methods

Maternal participants will be recruited via OB provider schedules at Ahuja Rainbow Center for Women and Children (ARCWC- Midtown location) and MacDonald 1200. Women will be approached in person before or after clinic visits with the permission of the OB provider. The study may be introduced in a group setting (CenteringPregnancy) but all consent procedures will be individual and private.

Setting

Expectant women will be recruited at UHCMC locations ARCWC and Mac1200. The intervention itself is virtual so following the consent process and enrollment there will not be inperson contact (except for the optional interview which can be by telephone or in person as preferred).

Consent Process

Potential participants will be recruited as above and approached in person before or after clinic visits with the permission of the OB provider. Signed consent will be obtained in person following an informed consent procedure with time for questions. The potential participant's exam room is a private place and if this is not available, we will find an unused office or conference space to have a private consent process. Potential participants who are interested will discuss the research with a study team member using the informed consent document. Family or friends may join the discussion if the potential participant chooses, and all questions will be answered. The potential participant can decide to participate and sign the informed consent or can decide to not join or can think about it further and call the study team if she decides to join.

Sharing of Results with Research Participants

☑ Results will not be shared with research participants.

Results are very preliminary and the number of participants is small so to avoid identifiability we will not provide results.

☑ Results will not be shared with research participants' doctors

Study Design

A prospective block-randomized two arm unblinded cohort study.

Study Procedures

1- Intervention – study procedures. In summary these include receiving texts, completing surveys and interviews, and permitting review of the medical record.

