The study intervention is texting of health information from 28 weeks gestation or from time of enrollment (24-34 weeks) through one year postnatally. Participants will be block randomized to either Bright By Text or Team2BF. Blocks will be by CenteringPregnancy group for those in this program and in sequential blocks of the same number of participants for those in individual obstetrical care.

Those randomized to Bright By Text begin receiving texts as soon as they sign up, and those randomized to Team2BF begin receiving texts at 28 weeks or at the time of enrollment if after 28 weeks.

Bright By Text sends messages total from the first trimester through eight years postpartum, with 2-4 messages per week about a wide range of maternal and child health topics as outlined on their website; there are in total 8 messages about breastfeeding from the prenatal period to 4 months postpartum. Team 2BF includes 3-4 breastfeeding-supportive messages per time

interval, sent weekly from 28 weeks gestation through delivery, daily through 2 weeks postpartum, weekly from 2 to 10 weeks, and then monthly to one year. Other maternal health topics are not addressed.

We are not able to collect user interactions with the SMS system (were texts read or not, was message link clicked or not) within the TEAM2BF REDCap/Twilio system; Bright By Text does have ability to collect user interactions but there is no plan to collect this information for the research and no ability for the study team to receive or access it. For TEAM2BF, participants can text STOP ALL or STOP SO MANY (to receive only one message per time point [by week prenatally or by day postpartum]) and for Bright By Text, participants can text STOP at any time to discontinue receiving texts. At the point of any unsubscribe, and at the 6 months postpartum time point, the participant will be invited by text to participate in a 10-15 minute interview about their experience The interview will be audio recorded and the transcript destroyed once call notes are verified against the recording.

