Participants will use their own smartphones for the study. The smartphone is a device but it is not being studied. The text messages are being studied. Given the definition of software as a medical device (The term "Software as a Medical Device" (SaMD) is defined as software intended to be used for one or more medical purposes that perform these purposes without being part of a hardware medical device. Reference- https://www.fda.gov/medical-devices/digitalhealth-center-excellence/software-medical-device-samd), the text messaging does not appear to be SaMD because it is not being used to treat, diagnose, cure, mitigate or manage a condition or disease. There are no drugs involved in this study.

Additional Information

The program that is used for the TEAM2BF texting is currently Twilio via REDCap. Twilio, a third-party web service, allows SMS text messages to be sent via REDCap Links within the messages go to free content – most content is publicly available, and for those PDFs that are not publicly available, we have used a REDCap function called "Dashboard" that permits us to create an URL for each of the PDFs. Bright By Text (https://brightbytext.org/) is commercially available—when signing up, participants provide due date, zip code, language preference (English or Spanish) and phone number to the site. Research surveys will be sent from REDCap for all participants.

Regarding the study title: The CTSC funding submission long title, "A proposed randomized clinical trial of the effectiveness of a new breastfeeding-supportive texting program designed specifically for African-American/Black expectant women, as compared to a national maternal health texting program, on rates of exclusive breastfeeding at 2 months" has been added to both the Protocol and the Supplemental form. Due to the complexity and length of the formal title, we are requesting to retain the shorter title, "TOPS – Texting to Promote Breastfeeding," as the header in the informed consent. The reason for this request is that the population of interest may have low health literacy and may have negative perceptions of very academic descriptors; the study is the same and is described equally by both the short and long titles.

Community-Based Participatory Research – NA

International information – NA

References

- 1. American Academy of Pediatrics Section on Breastfeeding. Breastfeeding and the Use of Human Milk [Policy Statement]. Pediatr 2012; 129: e827–e841. doi:10.1542/peds.2011-3552

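### Team2BF content can reach control mothers, through shared CenteringPregnancy groups or the earlier Team2BF study, and no described measure records it

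*Combined protocol and SAP*

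**What the plan says.** **Allocation.** The Study Design section calls the trial "A prospective block-randomized two arm unblinded cohort study". Under Study Procedures, "Participants will be block randomized to either Bright By Text or Team2BF", and "Blocks will be by CenteringPregnancy group for those in this program". Women in individual obstetrical care are allocated in sequential blocks of the same size. Recruitment Methods adds: "The study may be introduced in a group setting (CenteringPregnancy) but all consent procedures will be individual and private".

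**Eligibility.** There are three maternal exclusions: minors, women committed to formula only, and "No mobile phone with text capability". None concerns Bright By Text use or earlier Team2BF exposure.

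**Earlier exposure.** The Background reports a previous study of the same library: "That work (TEAM2BF, STUDY20221270) demonstrated that expectant and delivered AA/B women found the text messaging process and content acceptable and helpful". Its sites and number of participants are not given.

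**Access to content.** Additional Information describes Bright By Text as commercially available. Team2BF is sent through REDCap and Twilio, with no public sign-up described. Of the Team2BF texts it says "Links within the messages go to free content"; most of that content is public, and each PDF that is not public was given its own URL. Hypothesis 1 sets a target of more than 75% "endorsement of friend and family referral".

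**Measurement.** Study Procedures says that user interactions cannot be collected for Team2BF, and that those for Bright By Text will not be collected and are not accessible to the team. No survey in the Study Timeline is described as asking about the other programme. The Data Analysis Plan does not mention cross-exposure.

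**The concern.** The Background gives the purpose of the comparison as learning whether message content affects breastfeeding initiation and exclusivity at 2 months. That requires the content to differ between the arms. If mothers from both arms sit in one prenatal group, know their allocation, and hold texts and links that are easily passed on, some controls may see Team2BF material. A control mother who took part in the earlier study has already had it.

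Either route raises the control rate if the library works, and so shrinks the observed difference. The trial is meant to give preliminary efficacy data. If its estimate is carried into a later trial, unrecorded exposure would be carried with it. Exposure not asked about during follow-up is hard to reconstruct afterwards.

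**Working it through.** **1. Unit of allocation.** Two readings are possible.
- *Women randomised within each CenteringPregnancy group.* A block is normally the set within which arms are balanced. The text speaks of participants being block randomised, the individual-care blocks are counted in participants, and the sample size has no design effect. All of this favours the first reading.
- *Whole groups assigned to one arm.* Nothing in words rules this out. It would remove most sharing within groups, but the sample size and analysis would then have to allow for clustering.

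The first reading is the more natural one, but it is an inference.

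**2. Routes into the control arm.** No route to enrol in Team2BF is described for a control mother. What remains is forwarded texts, shared links, and earlier participation in STUDY20221270. The eligibility criteria block none of these.

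Timing limits the first two. Take a mother enrolled by 28 weeks who delivers at 40 weeks (assumption), and take 2 months as 8 weeks:
- weekly prenatal intervals: 40 − 28 = 12
- daily intervals to 2 weeks postpartum: 14
- weekly intervals from 2 to 8 weeks: 8 − 2 = 6
- total 12 + 14 + 6 = 32, of which 20/32 = 62.5% fall after delivery

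For enrolment at 34 weeks the total is 6 + 14 + 6 = 26, with 20/26 = 77% after delivery. Most of the material is therefore sent after the period in which a prenatal group meets.

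**3. Route into the Team2BF arm.** Bright By Text runs from the first trimester and enrolment is at 24 to 34 weeks, so a woman may already subscribe when allocated to Team2BF, or sign up later. Bright By Text has 8 breastfeeding messages from the prenatal period to 4 months. At 3 to 4 messages per interval, Team2BF sends 32 × 3 = 96 to 32 × 4 = 128 by 2 months. Dual use adds little breastfeeding content. It matters mainly for Aim 4, which compares general health outcomes that Bright By Text addresses and Team2BF does not.

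**4. What is measured.** The surveys listed are demographics, feeding intentions, knowledge, self-efficacy, infant feeding, social support, maternal satisfaction, healthy development and a thank-you survey. None is described as covering the other programme. The items of the demographics, satisfaction and thank-you surveys are not shown. The interview, offered at any unsubscribe and at 6 months, is optional and is about the mother's experience in general.

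**5. Direction and size.** The plan gives no figure for cross-exposure. Its sample size of 36 per group (11% against 14%, SD 5 points, 80% power, alpha 0.05) comes back only as a one-sided comparison of means: 2 × (1.645 + 0.842)² × (0.05/0.03)² = 34.4, so 35, or 35.04 with the t distribution, which rounds up to 36. Then 36/0.90 = 40 per group. Neither step allows for sharing.

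If a share *c* of controls gains a fraction *f* of the Team2BF effect, the control rate becomes 0.11 + 0.03*cf* and the difference becomes 0.03(1 − *cf*). Any *cf* above zero moves it toward zero. The documents give no value for *c* or *f*, for the share of women in CenteringPregnancy, or for the size of the earlier study. The calculation stops at direction.

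**The case against.** **The unit is not stated.** This stands. If whole groups are allocated, the main sharing route largely disappears. That is a reason to state the unit; it does not affect the missing criterion on earlier participants.

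**The routes are unequal.** This also stands. A reader might infer that each arm can equally receive the other's programme. The documents show open access in one direction only. The referral target asks whether a mother would recommend the texts; it is not evidence that she forwards them to controls. Link content that is already public is open to controls in any case.

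**Randomisation balances earlier exposure.** In expectation it does, but balance does not remove the dilution. Among earlier participants the comparison becomes a second course of Team2BF against a first.

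**The trial could reveal it anyway.** A reader might infer that cross-exposure is undetectable. The documents do not go that far: some survey items are not shown and the interview might bring it out. What can be said is that no measure is described.

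**The sample size is the larger problem.** Correct. About 36 × 0.11 = 4 control events are expected. Treated as two proportions, 11% against 14% needs about 1,907 per group (two-sided), and 36 per group gives about 6% power. A null result would be uninformative with or without sharing. Cross-exposure still biases the point estimate, and it is cheap to record.

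**Conclusion.** The point holds as a cheap improvement. As written, the plan could enrol control mothers who already had the Team2BF library, most naturally seats both arms in one prenatal group, and describes no record of sharing. The effect on the primary difference is toward zero, if Team2BF works at all.

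The amount cannot be estimated. A reader might assume that 10% to 50% of controls gain the full benefit, which would cut the 3-point difference to 3 × 0.9 = 2.7 or 3 × 0.5 = 1.5 points. Nothing in the documents supports a share in that range or a full benefit, and the schedule, with most texts sent after delivery, argues against full benefit from sharing in a prenatal group. The conclusion rests on reading the block as containing both arms, except for the route through the earlier study, which holds on either reading.

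**What to change.** 1. In Study Procedures, state in one sentence whether women or whole CenteringPregnancy groups are allocated. If groups, the sample size and analysis must allow for clustering.
2. Add to the maternal exclusions: *took part in STUDY20221270*.
3. At enrolment, record *currently signed up to Bright By Text (yes/no)*. Recording is preferable to excluding these women: the sample is 80 women from two clinics, and dual use hardly touches the primary outcome.
4. In the 2-month survey, in both arms and after the feeding questions, add two yes/no items: whether the mother saw texts or links from the other programme, and whether she signed up to any other pregnancy or feeding text programme. In that position they cannot colour the primary outcome.
5. Report the answers by arm beside the primary result, as description. Keep the primary comparison by randomised arm, because exposure after randomisation is not a baseline factor.

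A separate estimate for women in individual care is not advised. It would split about 4 expected control events further, and it would confuse sharing with the model of care.

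Cost: a few otherwise eligible women are lost, and there are a few more survey items. The 2-month items may also remind mothers of the other programme while follow-up continues to 6 months.

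### Fixed, equal-size blocks in an unblinded trial with no concealment step leave some upcoming assignments foreseeable if recruiters learn earlier ones

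*Combined protocol and SAP*

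**What the plan says.** Study Design describes the trial as "A prospective block-randomized two arm unblinded cohort study". Study Procedures, item 1, says: "Participants will be block randomized to either Bright By Text or Team2BF". It then defines the blocks. For women in group care the rule is: "Blocks will be by CenteringPregnancy group for those in this program". All other women are handled by a second rule, which places them "in sequential blocks of the same number of participants for those in individual obstetrical care".

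Under Recruitment Methods, women are identified from provider schedules, and "Women will be approached in person before or after clinic visits with the permission of the OB provider". The same section adds: "The study may be introduced in a group setting (CenteringPregnancy) but all consent procedures will be individual and private". Under Consent Process, a study team member conducts the discussion, and a woman may take time and call back later.

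The protocol does not give:
- a numeric block size, or any variation in size;
- how the sequence is generated and who holds it;
- when the arm is revealed relative to consent and the enrollment surveys;
- whether recruiters are kept from knowing earlier assignments;
- whether both arms occur within one CenteringPregnancy group, or the whole group receives one arm.

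**The concern.** Blocking makes assignments predictable when three things are known: where the block starts, how long it is, and which arms have already been used. The stated rule makes the first two easier to work out, because one set of blocks follows a clinic group and the other runs in sequence at a constant size. The third depends on whether recruiters learn earlier arms. The design is unblinded, and the arms run on different systems: Team2BF through REDCap and Twilio, Bright By Text through sign-up on its own site (Additional Information). The study team also contacts women who unsubscribe, and the unsubscribe commands differ by arm. Nothing in the plan keeps this information from recruiters.

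A recruiter who can foresee the next arm could influence whom to approach and when. Eligibility runs from women who may breastfeed to women who intend to, so eligible women differ on a factor close to the main outcome.

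The trial is small enough for this to matter. With 40 women per arm, one woman is 1/40 = 2.5 percentage points. Moving one eventual exclusive breastfeeder from one arm to the other shifts the difference by 2 × 2.5 = 5 points. The Data Analysis Plan uses a rise from 11% to 14% (3 points) for sample size, and elsewhere calls 5 points clinically meaningful.

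**Working it through.** **Inputs from the protocol.** Two arms, with 80 women in total and 40 per group (Number of Research Participants; Data Analysis Plan). The plan's enrolment figure reproduces: 36 / 0.9 = 40 per group. Equal groups imply 1:1 allocation. The plan gives no block size and no figure for predictability, so there is nothing further of its own to reproduce.

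**Assumptions.** Block size *b* is 6, 8 or 10; these values are mine. Past arms and block boundaries are known to the recruiter, and blocks fill completely.

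**Reading 1: individuals permuted 1:1 within a block.** An assignment is certain once one arm's *b*/2 places are used up.

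- Share certain in advance = 1 / (*b*/2 + 1).
- Correct-guess rate, always guessing the arm with more places left = [*b*/2 + 2^(*b*−1) / C(*b*, *b*/2) − 1/2] / *b*.

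| Block size | Share certain | Of 80 women | Correct guesses |
|---|---|---|---|
| 6 | 1/4 = 25% | 20 | (3 + 32/20 − 0.5)/6 = 68.3% |
| 8 | 1/5 = 20% | 16 | (4 + 128/70 − 0.5)/8 = 66.6% |
| 10 | 1/6 = 16.7% | 13.3 | (5 + 512/252 − 0.5)/10 = 65.3% |

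The benchmark, when the next arm cannot be predicted, is 0% certain and 50% guessed. Over the wider range of 4 to 12, the certain share runs from 33.3% to 14.3% and correct guesses from 70.8% to 64.3%.

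**Reading 2: a whole block goes to one arm.** Every assignment after the first in the block is known, a share of (*b* − 1)/*b*: 5/6 = 83%, 7/8 = 87.5% and 9/10 = 90% for sizes 6, 8 and 10. The wording does not rule this reading out.

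**Would varying the block size help?** I simulated a recruiter who knows all past arms and the set of possible sizes, but not the size of the current block. Sizes were drawn with equal probability.

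| Sizes used | Share certain | Correct guesses |
|---|---|---|
| 2, 4, 6 | about 4% | about 70% |
| 4, 6, 8 | about 2% | about 68% |

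Varying the size removes nearly all the certainty but hardly changes the guess rate, because guessing the arm that is behind does not require knowing the block size. Withholding earlier assignments is what brings the guess rate back towards 50%.

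**The case against.** The strongest reply is that the protocol shows an omission and not a demonstrated leak. A reader might infer that recruiters see upcoming arms, but the documents do not say that. Unblinded does not mean that recruiters hold the list or know each earlier assignment. This stands, and the figures above are conditional on it.

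A reader might also infer that a CenteringPregnancy roster reveals the block exactly. It does not. Members must each meet the eligibility criteria and each consent or decline in private, so the number who enrol is not fixed by the roster. A partly enrolled group may never reach the point where assignments become certain. This stands too, and makes the certain shares less secure for those blocks.

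A third tempting inference is that staff grade a woman's feeding intention to steer her. The criterion is her own stated plan, and no section says that the recruiter also allocates. Any steering would have to work through whom staff approach and when.

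Finally, feeding intention and self-efficacy are measured at enrollment, and the main comparison controls for factors known to affect breastfeeding. Steering on intention could therefore be detected and partly adjusted for. The protection is limited: the covariates are not named, and at the plan's rates only 36 × 0.11 + 36 × 0.14 = 9 events are expected, too few to support many covariates.

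None of this supplies a concealment step, and the fixed, sequential blocks are a stated method, so the point is more than missing detail.

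**Conclusion.** The concern holds as a risk. If recruiters learn earlier assignments, the stated blocking leaves about 17% to 25% of assignments certain in advance for 1:1 permuted blocks of 6 to 10, and 83% to 90% if whole blocks of those sizes go to one arm. These shares rest on assumed block sizes, filled blocks and knowledge of past arms. They measure predictability and not bias in the breastfeeding rate, which the documents give no means of estimating. The documents do not support a conclusion that selection bias is present or that recruiters do foresee assignments. This is a cheap improvement worth making; the sample size does not change.

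**What to change.** Amend Study Procedures, item 1, as follows.

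1. State that individuals are randomised 1:1 within strata defined by care type (CenteringPregnancy or individual) and site.
2. Replace the fixed equal-size blocks with undisclosed, randomly varied blocks, for example 4, 6 and 8.
3. Have someone outside recruitment generate the list and load it in REDCap, which the trial already uses.
4. Reveal the arm only after signed consent and completed enrollment surveys.
5. Keep recruiters unaware of earlier assignments where feasible. This matters because step 2 alone leaves best guesses near 68% when past arms are known.

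If whole CenteringPregnancy groups are meant to receive one arm, say so, enrol and survey the group's members before its arm is revealed, and analyse by group.

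The cost is protocol wording, a new list and minor set-up work. The downside is a possible slight imbalance within a single CenteringPregnancy group, because blocks would no longer coincide with groups.
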